CLINICAL STUDY PROTOCOLInterventional Drug or Biologic

A Pilot Study on the Safety and Efficacy of Mavoglurant in Alcohol Drinking

Protocol Number

2000021703

Protocol Version 2.9

PRINCIPAL INVESTIGATOR:

Name: [name]

Department: Yale School of Medicine Dept of Psychiatry

[contact]

Email Address: [contact]

IND Number: #137044

IND Holder: [name] NCT Number: NCT03327792

Study Phase 1:

Confidentiality Statement: This document is a confidential communication of the study sponsor ([name], Yale University School of Medicine). Acceptance of this document constitutes agreement by the recipient that no unpublished information contained herein will be published or disclosed without the sponsor's prior written approval, except that this document may be disclosed to appropriate Institutional Review Boards under the condition that they are requested to keep it confidential.

REVISION HISTORY:

Revision #	Version Date
2.0	1/11/2021
2.1	7/9/2021
2.2	12/16/2021
2.3	3/28/2022
2.4	6/6/2022
2.5	8/1/2022
2.6	9/12/2022
2.7	3/07/23
2.8 2.9	6/15/23 10/26/23

1 Synopsis

Primary Objective

The purpose of this study is to evaluate interactions between a moderate dose of alcohol and a non-competitive antagonist of the metabotropic glutamate receptor subtype 5 (mGLUR5), mavoglurant, on pharmacokinetic, physiological or behavioral responses in healthy social drinkers.

Study Duration

6 years, plus 1 year for data analysis

Study Design

This pilot study will examine interactions between alcohol and mavoglurant and explore the effects of mavoglurant on alcohol responses. This is a between subjects, double-blind design. We propose to recruit 40 male and female healthy volunteers (to achieve a completer sample of 28 participants) who meet criteria for social drinking (i.e., consuming 1- 6 standard alcoholic drinks per week and having engaged in at least one and no more than 12 binge drinking episodes in the past year), do not meet criteria for a DSM-V Alcohol Use Disorder, and who are willing to abstain from alcohol during the outpatient study medication treatment phase.

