8.1 General Design Description

Double blind placebo-controlled trial of mavoglurant vs. placebo in light social drinkers (i.e., consuming 1- 6 standard alcoholic drinks per week and having engaged in at least one and no more than 12 binge drinking episodes in the past year). Participants will not meet criteria for a DSM-V Alcohol Use Disorder and must be willing to abstain from alcohol during the outpatient medication treatment phase. We propose to recruit 40 male and female social drinkers (to achieve a completer sample of 28 participants).

Subjects will sign informed consent and eligibility will be determined. Eligible subjects will participate in two alcohol administration lab sessions. They will be randomized to receive either 200 mg/day of mavoglurant or placebo for 7-10 days (14 in each study arm). During the outpatient medication administration phase, subjects will be observed daily as their medication is administered. Adverse events will be assessed. The first lab session will occur on Day 0 (prior to start of study medication) and the second lab session will occur following 7-10 days (as scheduling permits) of study medication. During each lab session, subjects will receive six successive doses of alcohol over a 90-min period designed to raise their blood alcohol levels to 80 mg/dl. Outcomes will include adverse events (during outpatient period and the lab session), safety labs (before and after drug and after alcohol), PK/PD of drug and alcohol, behavioral tests of cognition and body sway as well as self-reports of intoxication and other alcohol effects. Study staff will check in with subjects on the two days following the second lab session and an in-person follow up appointment will be scheduled 1 week after the second lab session.

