8.2.1 Secondary Outcome Variables (if applicable)

The secondary outcomes are blood alcohol levels on mavoglurant compared to no drug, and drug levels of mavoglurant before and after alcohol administration.

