8.2.2 Exploratory Outcome Variables (if applicable)

Alcohol effects on stimulation, sedation, intoxication (Biphasic Alcohol Effects Scale), cognitive motor performance and physiological responses (blood pressure and heart rate) measured during the mavoglurant session and compared to responses measures during the baseline no-drug session.

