9.5 Planned Analyses

9.5.1 Primary Objective Analysis

Adverse events will be tabulated and rated for severity (mild, moderate, and severe) and for relation to the study intervention (unlikely, possibly, probably, and likely). Area under the curve will be measured for blood alcohol levels and compared between the two sessions (mavoglurant; baseline no-drug). Changes in serum chemistries, blood cell counts, and urinalysis will be compared before and after alcohol consumption between sessions (on drug, baseline no-drug). Quantitative outcomes will be analyzed using mixed models.

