9.5.3 Exploratory Objectives Analyses (if applicable)

Changes in subjective and cognitive motor performance measures following alcohol consumption will also be compared between sessions (on drug, baseline no-drug).

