9.5.5 Analysis of Subject Characteristics

Subject demographics will be collected and reported, noting any differences between active/placebo groups.

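### The written outcome contrasts compare the on-drug session with the earlier no-drug session, so no outcome gets a mavoglurant-versus-placebo comparison

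*Combined protocol and SAP*

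**What the plan says.** The Synopsis describes the design in these words: "This is a between subjects, double-blind design". Section 8.1 randomises participants to mavoglurant or placebo, 14 per arm, and fixes the order of sessions: "The first lab session will occur on Day 0 (prior to start of study medication"). Session 2 follows 7 to 10 days of the assigned treatment in both arms.

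The contrasts written for the outcomes are these:

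- Blood-alcohol AUC (9.5.1): "Area under the curve will be measured for blood alcohol levels and compared between the two sessions (mavoglurant; baseline no-drug").
- Serum chemistry, cell count and urinalysis changes (9.5.1): "will be compared before and after alcohol consumption between sessions (on drug, baseline no-drug").
- Subjective and cognitive-motor changes (9.5.3): "will also be compared between sessions (on drug, baseline no-drug").
- The outcome definitions agree. Section 8.2.1 has "blood alcohol levels on mavoglurant compared to no drug", and 8.2.2 has the mavoglurant session "compared to responses measures during the baseline no-drug session".

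Adverse events are tabulated by severity and relatedness, with no comparison of arms stated. Section 9.5.1 closes by assigning quantitative outcomes to mixed models without listing any terms. Arms are compared in only two places, and neither concerns a listed outcome: demographics (9.5.5, "noting any differences between active/placebo groups") and dropout (9.5.10).

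**The concern.** A placebo arm is there to remove everything that differs between the two sessions apart from the drug. Here Session 2 is a second alcohol challenge, it follows a period of requested abstinence (9.3), and the body sway, CPT and reaction-time tasks are being repeated (9.3.5). A contrast of Session 2 with Session 1 credits any such change to mavoglurant, or lets it hide a mavoglurant effect. Hiding an effect is the worse error in a study whose primary objective is the safety of the combination.

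Section 9.4.1 says the pilot is meant to supply effect sizes for larger studies. As written, those would be session differences, although a randomised control group is available.

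The labels also leave the placebo participants with no place. Their second session is neither a mavoglurant session nor on drug, so an analyst following the text must either omit them or mislabel them.

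**Working it through.** **Plan's own figure.** There is none to reproduce. Section 9.4.1 states that no power calculation was done, and no alpha, SD or effect size is given. The only input taken from the documents is 14 completers per arm, 28 in total (8.1). Everything else below is an assumption: two-sided 0.05, normally distributed data, and the stated session shifts and correlations.

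**What the session contrast estimates.** Let δ be the drug effect at Session 2 and σ the non-drug change from Session 1 to Session 2.

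- Mavoglurant arm only: δ + σ.
- Both arms pooled, 14 and 14: (14(δ + σ) + 14σ)/28 = δ/2 + σ.
- Difference between arms: (δ + σ) − σ = δ.

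With σ = 0 and δ = 0.50 SD, pooling returns 0.25 SD. For outcomes first differenced before and after alcohol within a session, a constant session-level shift cancels, and σ is only the non-drug change in the response to alcohol. Blood-alcohol AUC is not differenced, so any session shift counts in full.

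**False positives with δ = 0.** The power of a paired t test has noncentrality d√n, where d is the shift in SDs of the paired difference.

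| Shift d | n=14: d√14 | Rejects | n=28: d√28 | Rejects |
|---|---|---|---|---|
| 0.1 | 0.374 | 6% | 0.529 | 8% |
| 0.3 | 1.122 | 18% | 1.587 | 33% |
| 0.5 | 1.871 | 41% | 2.646 | 72% |

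In 40,000 simulated trials at session correlation 0.5, an arm comparison adjusted for Session 1 rejected 5.0% and 4.9% of the time at shifts of 0.3 and 0.5.

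**Masking.** A true effect of 0.8 SD of the paired difference is detected within the mavoglurant arm in 79% of trials (n=14). An opposite shift of 0.3 leaves 0.8 − 0.3 = 0.5, detected in 41%. An opposite shift of 0.5 leaves 0.3, detected in 18%.

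**Precision.** The standard errors, in SDs of the outcome with session correlation ρ, are:

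- adjusted arm difference: √((2/14)(1 − ρ²))
- arm-by-session: √((2/14)·2(1 − ρ))
- within arm: √(2(1 − ρ)/14)
- pooled: √(2(1 − ρ)/28)

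| Contrast (df) | SE, ρ=0.3 | SE, ρ=0.8 | 95% half-width, ρ=0.3 to 0.8 |
|---|---|---|---|
| Adjusted arm difference (25) | 0.361 | 0.227 | 0.74 to 0.47 |
| Arm-by-session (26) | 0.447 | 0.239 | 0.92 to 0.49 |
| Within arm (13) | 0.316 | 0.169 | 0.68 to 0.37 |
| Pooled (27) | 0.224 | 0.120 | 0.46 to 0.25 |

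The ratio of adjusted to within-arm SE is √(1 + ρ) = 1.14 to 1.34. Adjusted to pooled is √(2(1 + ρ)) = 1.61 to 1.90.

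**Power of the arm comparison.** For the same 0.8 SD effect of the paired difference, the adjusted comparison has noncentrality 0.8√(14/(1 + ρ)) = 2.625, 2.444 and 2.231 at ρ = 0.3, 0.5 and 0.8. That gives about 71%, 65% and 57%. Arm-by-session has 0.8√7 = 2.117, about 53%.

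**Laboratory draws.** Section 6.1.1 gives 70.5 cc at Session 1 and 85.5 cc at Session 2. These equal 50 + 5.5 + 15 and 50 + 5.5 + 2 × 15, so there is one 50 cc safety draw per session. The stated total of 306 ml equals 50 + 70.5 + 85.5 + 50 + 50, which leaves room for one morning-after draw. The appendix session sheet puts the health profile at 11:00, before the first drink, and 9.3.1 and 9.3.5 show a morning-after draw only after Session 2. On that schedule Session 1 has no post-alcohol safety laboratory value, and the laboratory contrast in 9.5.1 cannot be computed. Section 9.2(h) points the other way: it places panels on the morning after the lab sessions, in the plural.

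**The case against.** The strongest reply is that the plan is incomplete and not wrong. The trial is labelled placebo-controlled and between-subjects, and a mixed model with arm and session terms may well be what the team intends. That is possible, and reading the text as an omission is fair to its authors. But no such term is written, while the session contrast is written in four sections. Anyone following the document would run the session contrast.

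Other points stand in part:

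- Pooling is the less natural reading, because on drug does not describe placebo recipients. The 33% and 72% figures depend on it. The within-arm figures do not.
- The plan sets no alpha and calls itself exploratory, and both sessions use the same fixed alcohol dose, so the rejection rates illustrate a test that it never states. The bias in the estimated effect size needs no test and is the firmer argument.
- The arm comparison is less powerful than an unbiased within-arm contrast would be: about 57% to 71% against 79% for the effect above. The 79% holds only if there is no session shift, which the within-arm data cannot show.
- Section 9.2(h) conflicts with the schedule on Session 1 laboratory draws, so that point is not settled. The proposed analysis works on either reading.

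**Conclusion.** The concern holds and should be fixed before analysis. Three sets of outcomes are assigned a fixed-order session contrast in a randomised placebo-controlled trial, adverse events are assigned no contrast, and no outcome is assigned a comparison of arms. That the written contrast confounds drug with session follows from the text and needs no assumption. The size does: the documents give no session shift. If there were none, the within-arm estimate would be unbiased and the pooled estimate would be half the drug effect. Shifts of 0.3 to 0.5 SD of the paired difference would raise the within-arm false-positive rate to 18% to 41% at two-sided 0.05, or cut detection of a 0.8 SD effect from 79% to between 41% and 18%.

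**What to change.** - In 8.2.1 (blood alcohol), 8.2.2, 9.5.1 and 9.5.3, name the mavoglurant-minus-placebo difference at Session 2, with its 95% confidence interval, as the estimand.
- Estimate it with a mixed model, or a linear model for AUC, adjusted for the Session 1 value of the same outcome. List the terms. An arm-by-session test is also valid but usually less precise, so choose one in advance.
- For safety laboratories, state which draw is the outcome (Session 2 before alcohol, the morning after, or each) and whether it is analysed as a level or a change. Adjust for the Session 1 pre-alcohol value. Reconcile 9.2(h) with 9.3.1, 9.3.5 and the blood volumes in 6.1.1.
- Tabulate adverse events by arm. Keep within-arm session contrasts as descriptive. Leave the drug-level comparison in 9.5.2 as it is.
- Date the amendment and make it before outcome data are unblinded. Section 7.2 reports 24 completers (10 + 14) and says that mavoglurant levels from the first 10 have been analysed. Such levels can reveal the arm, so the amendment should record who has seen them.

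The cost is a change of analysis wording, with IRB approval (10.2) and FDA notification (10.13), and no new data. The standard error is 14% to 34% larger than within arm and 61% to 90% larger than pooled, and the 95% half-width is about 0.74 to 0.47 SD of the outcome for correlations of 0.3 to 0.8. Report that width with the estimates, because it shows how much 14 per arm can say.

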6.1 Purpose of Study/Potential Impact

The purpose of this study is to evaluate the safety and tolerability of a moderate dose of alcohol in combination with a non-competitive antagonist of the metabotropic glutamate receptor subtype 5 (mGLUR5), mavoglurant, on pharmacokinetic, physiological or behavioral responses in healthy social drinkers.

Prior to initiating a study to examine the influence of mavoglurant on drinking behaviors in heavy drinkers, we propose to conduct this study to examine the safety and pharmacokinetic interactions of administering mavoglurant and alcohol together.

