7.2 Secondary Objectives (if applicable)

Specific Aim 2: To evaluate the interactions of alcohol and mavoglurant on blood alcohol levels and mavoglurant levels.

We collected and analyzed mavoglurant levels from the first 10 participants who completed this study. These results did not show any changes in mavoglurant levels after alcohol administration. We collected blood sample from the additional 14 participants who recently completed the study but at present we do not have the funding to complete these assays which are rather expensive and can only be conducted by one company in India. So we would like to not conduct these assays on the new samples but we would like to retain the deidentified samples and conduct the assays at a later date if and when funding becomes available

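### Blood alcohol exposure is only to be compared between sessions, with no ratio, interval or placebo-controlled contrast, so a non-significant result could be misread as no interaction

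*Combined protocol and SAP*

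**What the plan says.** Section 6.1 gives the purpose: before a study in heavy drinkers, to "examine the safety and pharmacokinetic interactions of administering mavoglurant and alcohol together". Section 9.4.1 describes an exploratory study that is to yield effect sizes and to determine whether the two substances can be used together safely. Aim 2 in section 7.2 is "To evaluate the interactions of alcohol and mavoglurant on blood alcohol levels and mavoglurant levels".

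The design is randomised: "This is a between subjects, double-blind design" (Synopsis), "to achieve a completer sample of 28 participants", with "14 in each study arm" (section 8.1). Each participant has one alcohol session before study medication and one after 7 to 10 days of it.

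The analysis of the alcohol half of Aim 2 is one sentence in section 9.5.1: "Area under the curve will be measured for blood alcohol levels and compared between the two sessions". The sessions are labelled there as mavoglurant and baseline without drug. The same section adds "Quantitative outcomes will be analyzed using mixed models". Section 8.2.1 uses the same contrast: "The secondary outcomes are blood alcohol levels on mavoglurant compared to no drug". It lists the outcome as secondary, whereas 9.5.1 analyses it under the primary objective.

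No section states the scale of AUC, its time window, the fixed effects, an interval estimate, a size of interaction that would matter, or how a null comparison would be interpreted.

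**The concern.** The next study needs to know how large a change in alcohol exposure on mavoglurant can be excluded. Alcohol is dosed towards 80 mg/dl, which sections 6.1.1 and 9.3 call the legal limit of intoxication, so a rise in exposure would matter. A comparison reported only as significant or not does not answer that question. With 14 per arm, a non-significant result may be compatible with a material rise.

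The risk of misreading is plausible. For the other half of the same aim, section 7.2 already reports that mavoglurant levels in the first 10 completers did not change after alcohol, with no estimate or interval.

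The stated contrast has a second weakness. Session 2 always follows Session 1, so on-drug against baseline mixes the drug effect with any effect of session order or familiarity. The placebo arm can separate the two, but section 9.5.1 does not say that it will be used for this.

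**Working it through.** **Inputs from the documents.** 28 completers, 14 per arm (section 8.1), and two sessions per participant. There is no power or precision figure to reproduce: section 9.4.1 says none was calculated, and no alpha, CV or margin is given.

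**Assumptions, not in the documents.** Within-person CV of AUC between 10% and 30%, equal in both arms; complete data; illustrative limits of 0.80 to 1.25; a two-sided 5% test where a test is considered.

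**Randomised contrast (arm by session).** Take each person's change in ln(AUC), Session 2 minus Session 1, and compare the arms.

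- Within-person variance on the log scale: ln(1 + CV²).
- SD of the change: √(2 × ln(1 + CV²)).
- SE of the log ratio of ratios: SD × √(1/14 + 1/14), with 26 df.
- 90% CI: ratio multiplied and divided by exp(1.706 × SE).

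Example at CV 15%: ln(1.0225) = 0.02225; SD = √0.0445 = 0.211; SE = 0.211 × 0.378 = 0.0797; half-width = 1.706 × 0.0797 = 0.136; factor = exp(0.136) = 1.15.

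The chance that the CI lies inside the limits comes from 400,000 simulated trials with a true ratio of 1. The chance of a non-significant test at a true ratio of 1.25 comes from the noncentral t distribution.

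| Assumed CV | SE | 90% CI factor | CI inside 0.80–1.25, true ratio 1 | Test non-significant, true ratio 1.25 |
|---|---|---|---|---|
| 10% | 0.053 | 1.10 | 98% | 2% |
| 15% | 0.080 | 1.15 | 72% | 23% |
| 20% | 0.106 | 1.20 | 32% | 47% |
| 25% | 0.132 | 1.25 | 8% | 63% |
| 30% | 0.157 | 1.31 | 1% | 72% |

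**Contrast as literally worded (Session 2 against Session 1, mavoglurant arm only, n = 14).** SE = SD/√14, with 13 df.

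| Assumed CV | 90% CI factor | CI inside 0.80–1.25, true ratio 1 | Test non-significant, true ratio 1.25 |
|---|---|---|---|
| 10% | 1.07 | 100% | 0% |
| 15% | 1.11 | 96% | 5% |
| 20% | 1.14 | 76% | 21% |
| 25% | 1.18 | 47% | 40% |
| 30% | 1.22 | 24% | 54% |

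This version is tighter by a factor of √2 in SE, but only because it assumes that there is no session effect. Any such effect goes straight into the estimate.

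**Smaller sample.** Section 7.2 mentions 10 + 14 = 24 completers. With an assumed 12 per arm, the randomised-contrast factors become 1.10, 1.16, 1.22, 1.28 and 1.34, and the chances of lying inside the limits become 96, 61, 21, 4 and 0.5%.

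**The case against.** The strongest reply is that this is an exploratory pilot. Section 9.4.1 asks for effect sizes, which points to estimation and not to testing, and a formal no-interaction margin is a confirmatory device. That stands in part: neither a power calculation nor a margin should be demanded. But a ratio with its interval is an effect size, so specifying one serves the stated aim.

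Four stronger readings are tempting, and the documents do not support them.

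- A reader might infer that non-significance is to be taken as no interaction. No section says so. The remark in section 7.2 concerns drug levels, not alcohol, and shows only that the misreading is plausible.
- A reader might infer that AUC will be analysed untransformed with a 5% test. Section 9.5.1 states neither scale nor alpha.
- A reader might apply the 2, 23 and 47% miss rates at CV 10, 15 and 20% to the plan's own comparison. They belong to the arm-by-session contrast. For the literal within-arm contrast the figures are 0, 5 and 21%.
- A reader might infer that the placebo arm will be left out. The mixed model may include arm, and the Synopsis calls the design between-subjects. The plan simply does not name the contrast.

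It is also fair to object that 28 completers may not settle the question. On the assumed CV range the answer runs from near-certain to almost hopeless, and 0.80 to 1.25 is only an illustration.

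**Conclusion.** The point holds as a defect in the planned analysis and reporting. Section 9.5.1 does not commit the trial to a placebo-controlled estimate of the change in alcohol exposure, or to any statement of its uncertainty, although the combination's safety is the reason for the study. A non-significant comparison could therefore be misread as no interaction.

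Better specification makes the uncertainty visible but does not guarantee a conclusive result. With 14 per arm, the 90% CI factor runs from 1.10 at CV 10% to 1.31 at CV 30%. For limits of 0.80 to 1.25, the chance of excluding a change of that size when there is none falls from 98% to 1%. The trial is well placed if the CV is near 10%, and poorly placed from about 20% upwards. All of this rests on a CV and limits that the documents do not give, so it cannot be said in advance that the trial will or will not exclude a particular size.

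**What to change.** Replace the AUC sentence in section 9.5.1 with a specification on these lines.

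- **Outcome.** ln(AUC) of blood alcohol over a stated window. The sampling times need reconciling first. Section 9.3 gives a baseline sample, one every 15 minutes, then hourly for three hours; if the 15-minute samples cover the 90 minutes of drinking, that is 1 + 6 + 3 = 10. The appendix and the blood-draw table in 6.1.1 give 11, and the appendix puts the last at 300 minutes.
- **Model.** Mixed model with arm, session and arm-by-session.
- **Main result.** The mavoglurant/placebo ratio of the Session 2 to Session 1 geometric mean ratios, with its 90% CI.
- **Interpretation.** Non-significance will not be taken as absence of interaction.
- **Limit, only if wanted.** If the investigators wish to claim no relevant interaction, they should set and document the limit before unblinding. If the CI crosses it, the result is reported as inconclusive. Under section 9.1.4 the study biostatisticians can see the allocation, so someone without that access should set it. That person should also not have seen individual mavoglurant levels, which could reveal the arm.

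The secondary status in 8.2.1 and the placement under the primary objective in 9.5.1 should be reconciled at the same time.

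No new data are needed, since the samples are already scheduled. The cost is wording, a dated record of any limit, and accepting that the trial may have to report an inconclusive result.
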